Objectives:	
Primary Objective: To determine the efficacy of incentive spirometry to improve FEV1 in the preoperative surgical setting.
 
Secondary Objectives:
 
 1. To determine the efficacy of incentive spirometry to improve FVC and pulse oximetry in the preoperative surgical setting. 2. To determine the change in FEV1, FVC and pulse oximetry after surgery. 
Exploratory Objectives:
 
 1. To determine the daily number of times patients perform incentive spirometry in the preoperative and postoperative setting. 2. To determine whether standard incentive spirometers move throughout a patients' postoperative stay using accelerometers, as a proxy for how often patient uses the device. 3. To evaluate whether a digital IS device + text message based mobile health intervention will improve FEV1, FVC, and pulse oximetry compared to standard IS. 4. To evaluate the rate of pulmonary complications across the 3 preoperative groups.
Endpoints:	
Primary Endpoint: Change in FEV1 at day-of-surgery preoperative from baseline
 
Secondary Endpoints:
 
 1. Change in FVC and pulse oximetry at day-of-surgery preoperative from baseline 2. Change in FEV1, FVC and pulse oximetry at postoperative day 3 from day 1

	
Exploratory Endpoints:
 
 1. Daily frequency of digital IS use. 2. Movement data of standard IS with accelerometers (this is a proxy endpoint for IS use). 3. Difference in changes in FEV1, FVC, and pulse oximetry between randomized groups. 4. Postoperative complications defined by Modified Accordion Grading System (MAGS)
Study Population:	We plan to enroll 156 adult patients who are scheduled to undergo major abdominal surgery with an expected postoperative hospital stay of \geq 48 hours.
Phase:	N/A
Description of Sites / Facilities Enrolling:	The study will take place at Barnes Jewish Hospital system/Washington University School of Medicine.

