1.0 INTRODUCTION

1.1 Background/Rationale

Recent developments in perioperative care, like the development of enhanced recovery pathways, have been designed to decrease practice variability and achieve early recovery after surgery to decrease the postoperative length of hospitalization for patients.¹⁻⁵ Despite this, there has not been a significant reduction in postoperative readmissions.⁶⁻⁸ The complication rate after major abdominal surgery such as pancreaticoduodenectomy and liver resection continues to be up to 50%.⁸⁻¹⁰ Most research aiming to improve postoperative outcomes has focused on postoperative interventions, but in the last couple of years, there has been significant interest in developing interventions that address the preoperative period.¹¹⁻¹⁸ One specific intervention that has been proposed with limited and variant support is the use of incentive spirometry (IS). IS involves using a device to facilitate deep breathing exercises to increase lung capacity and open airways with the goal to prevent pulmonary complications.¹⁹⁻²³

IS has had widespread implementation in the United States in the **postoperative** period although there is limited data supporting its efficacy in clinical trials. A systematic review by Overend et al. evaluated 46 studies to ascertain the effect of postoperative IS on the incidence of postoperative complications, but failed to show a positive effect for postoperative IS.²⁴ More recently, Zoremba et al. evaluated the effect of IS in the postoperative recovery unit on lung function for obese patients undergoing a variety of non-abdominal surgical procedures.²⁵ They did not find significant differences in pulse oximetry and pulmonary function tests (PFTs) immediately after surgery, but at all subsequent time points—1, 2, 6, and 24 hrs after surgery—SpO₂, FVC, FEV1 and PEF were higher for the IS group. In summary, data regarding postoperative IS use is sparse and inconsistent.

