2.0 OBJECTIVES AND ENDPOINTS

Objectives	Endpoints	Justification for Endpoints
Primary		
To determine the efficacy of incentive spirometry to improve FEV1 in the preoperative surgical setting.	Change in FEV1 at day-of-surgery preoperative from baseline	

Secondary		

3. To determine the efficacy of incentive spirometry to improve FVC and pulse oximetry in the preoperative surgical setting.
 
4. To determine the change in FEV1, FVC and pulse oximetry after surgery.
	
1. Change in FVC and pulse oximetry at day-of-surgery preoperative from baseline
 
2. Change in FEV1, FVC and pulse oximetry at postoperative day 3 from day 1
	
Tertiary/Exploratory		

1. To determine the number of times patients perform incentive spirometry in the preoperative and postoperative setting.
 
2. To determine whether standard incentive spirometers move throughout a patients' postoperative stay using accelerometers, as a proxy for how often patient uses the device..
 
3. To evaluate whether a digital IS device + text message based mobile health intervention will improve FEV1, FVC, and pulse oximetry compared to standard IS.
 
4. To evaluate the rate of pulmonary complications across all 6 groups.
	
1. Daily frequency of IS use
 
2. Postoperative complications defined by Modified Accordion Grading System (MAGS)
	

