9.0 STATISTICAL CONSIDERATIONS

9.1 Study Design

This is a prospective, single-center, randomized trial. The enrolled patients will be randomized 1:1:1 to one of three groups: control, standard IS, and digital IS + text message. They will have baseline measurement at the time of randomization, and pre-operative measurement after randomization and before the surgery. After surgery, patients will be re-randomized to either standard IS or digital IS + text message. Measurements at post-op days 1 and 3 will be taken. The primary objective of this study is to determine the efficacy of incentive spirometry to improve FEV1 in the preoperative setting. The secondary objectives are to determine the efficacy of incentive spirometry to improve FVC and pulse oximetry in the preoperative setting, and FEV1, FVC, and pulse oximetry in the postoperative setting. The exploratory objectives are to determine the daily number of times patients perform incentive spirometry in the postoperative setting and evaluate the rate of pulmonary complications across the 3 preoperative groups.

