9.4 Endpoints

The primary endpoint is FEV1 change at day-of-surgery preoperative from baseline. The secondary endpoints include FVC and pulse oximetry change at day-of-surgery preoperative from baseline, change in FEV1, FVC and pulse oximetry at preoperative day 3 from day 1. Exploratory Endpoints are daily frequency of IS use and postoperative complications defined my Modified Accordion Grading System (MAGS).³⁹

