9.6 Data Analysis

The analysis will be intent-to-treat approach. The FEV1, FVC and pulse oximetry changes at day-of-surgery preoperative from baseline will be compared across three groups using ANOVA or Kruskal-Wallis test, as appropriate. The linear regression model will be considered to adjust for the other interested variables including age, sex, smoking status, BMI, ASA, and malignancy. The same analysis method will be conducted for FEV1, FVC and pulse oximetry changes at preoperative day 3 from day 1. The frequency of use, defined as the daily number of times patients perform incentive spirometry, will be compared across all groups in the postoperative setting using ANOVA or Kruskal-Wallis test, as appropriate. For postoperative complications, Chi-square test will be used to test the differences between six groups. The univariate logistic regression model will estimate the odds ratio of postoperative complication. Multivariate analysis through stepwise selection will be considered to examine the relationship between binary outcome and independent predictors, where a significance level of 0.3 is required to allow a predictor into the model, and a significance level of 0.35 is required for a predictor to stay in the model. All analyses will be conducted using SAS (SAS Institute, Cary, NC) at the two-sided 5% significance level.

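### The exploratory objective asks for the rate of pulmonary complications, but its endpoint and the complication analyses named in Section 9.6 carry no pulmonary restriction

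*Combined protocol and SAP*

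**What the plan says.** The objective appears three times, each time limited to pulmonary events. The Synopsis has "To evaluate the rate of pulmonary complications across the 3 preoperative groups"; the table in Section 2.0 has "To evaluate the rate of pulmonary complications across all 6 groups"; Section 9.1 again has "evaluate the rate of pulmonary complications across the 3 preoperative groups".

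The endpoint also appears three times, and never with that limit. The Synopsis and the Section 2.0 table both give "Postoperative complications defined by Modified Accordion Grading System (MAGS" as the endpoint, and Section 9.4 repeats it.

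Section 9.6 keeps the broader scope: "For postoperative complications, Chi-square test will be used to test the differences between six groups", followed by "The univariate logistic regression model will estimate the odds ratio of postoperative complication". It then describes a stepwise multivariate model for a binary outcome that it does not identify.

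Section 5.0 says that general postoperative outcomes, complications among them, are collected under a divisional protocol that is not reproduced. No section lists the events that count as pulmonary.

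**The concern.** An objective should lead to an endpoint, and the endpoint to an analysis, that measure the same thing. Here the objective names one class of complication, while the endpoint and analysis name a wider class that contains it.

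The narrower class is the one the intervention is meant to affect. Section 1.1 describes IS as a way to increase lung capacity and "open airways with the goal to prevent pulmonary complications". If preoperative IS prevents pulmonary events and leaves leaks, wound infections and the like unchanged, the unchanged events add to both arms and dilute the contrast. A reader of the final report could then see little difference in complications and take it as an answer to the pulmonary question, which the named analyses had not addressed.

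There is a second risk. With no list fixed beforehand, anyone who later tabulates pulmonary events must decide after the data are in which events qualify. With few events, that choice can change the result.

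**Working it through.** **1. The plan's own figure.** The only design calculation (Section 9.5) is for FEV1: 49 per group, difference 0.4 L, SD 0.6, two-sided level 0.017. The noncentrality is 0.4 / (0.6 × √(2/49)) = 3.30 and the critical t on 96 degrees of freedom is 2.43, giving power 80.6%, as stated. Dropout: 49 / 0.95 = 51.6, so 52 per group and 156 in all. None of this depends on the complication outcome, and the plan gives no planning rate for complications.

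**2. The text side by side.**

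| Place | Role | Scope |
|---|---|---|
| Synopsis, exploratory objective 4 | Objective | Pulmonary |
| Section 2.0, exploratory objective 4 | Objective | Pulmonary |
| Section 9.1 | Objective | Pulmonary |
| Synopsis, exploratory endpoint 4 | Endpoint | Postoperative, MAGS |
| Section 2.0 table | Endpoint | Postoperative, MAGS |
| Section 9.4 | Endpoint | Postoperative, MAGS |
| Section 9.6, chi-square | Analysis | Postoperative |
| Section 9.6, logistic odds ratio | Analysis | Postoperative |
| Section 9.6, stepwise model | Analysis | Not stated |

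The word pulmonary does not occur in Section 9.4 or 9.6. Section 9.6 does not mention MAGS either, and it gives no grade at which a complication becomes an event.

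**3. Illustration of the dilution (assumed rates).** Section 1.1 gives one relevant figure, an overall complication rate of up to 50% after operations such as pancreaticoduodenectomy and liver resection. The rest is assumed: a control pulmonary rate p of 10–20%, an other-complication rate q of 20–37.5% that is independent of it, and IS halving p and leaving q alone. The broader outcome is read as any complication against none.

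Control any-rate: A = 1 − (1 − p)(1 − q). IS any-rate: B = 1 − (1 − p/2)(1 − q). Odds ratio: [B/(1 − B)] / [A/(1 − A)]. The pulmonary odds ratio uses p/2 and p in place of B and A.

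| p | q | A | B | OR, any | OR, pulmonary |
|---|---|---|---|---|---|
| 0.10 | 0.20 | 0.280 | 0.240 | 0.81 | 0.47 |
| 0.10 | 0.375 | 0.438 | 0.406 | 0.88 | 0.47 |
| 0.15 | 0.30 | 0.405 | 0.353 | 0.80 | 0.46 |
| 0.20 | 0.20 | 0.360 | 0.280 | 0.69 | 0.44 |
| 0.20 | 0.375 | 0.500 | 0.438 | 0.78 | 0.44 |

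Independence may understate the dilution. If 60% of pulmonary cases also have another complication, halving p lowers the any-rate by only 0.4p/2. With (p, A) of (0.10, 0.40), (0.15, 0.45) and (0.20, 0.50), the any-complication odds ratios are 0.92, 0.89 and 0.85.

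**4. How many events there would be.** With 52 per group, expected pulmonary events are 52p = 5.2–10.4 in control and 52p/2 = 2.6–5.2 in each IS arm, so 10.4–20.8 in total. In the independent scenarios, the share of counted patients with no pulmonary event runs from (47.8 − 20.8)/47.8 = 57% (p = q = 0.20) to (65.0 − 10.4)/65.0 = 84% (p = 0.10, q = 0.375).

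For one IS arm against control, the variance of the log odds ratio is the sum of the reciprocals of the four expected counts. At p = 0.10 this is 1/5.2 + 1/46.8 + 1/2.6 + 1/49.4 = 0.619 (SE 0.786), so the 95% interval is 0.47 (0.10–2.21). At p = 0.20 it is 0.44 (0.14–1.38). For any complication it is 0.88 (0.40–1.92) at p = 0.10, q = 0.375, and 0.69 (0.30–1.58) at p = q = 0.20.

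**The case against.** The best defence is that the wording is loose. The Synopsis gives both the objective and the endpoint as item 4, so one can read the objective as supplying the type of event and MAGS as supplying the grade. On that reading pulmonary is implied throughout. Nothing in the endpoint, data-collection or analysis text says so, however, and an analyst who accepted it would still have no event list. The edit is needed either way.

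A second defence is that the adjective in the objective is the slip. The endpoint and Section 9.6 agree with each other, and Section 1.1 discusses overall complications and morbidity as well as pulmonary events. This stands: the documents do not show which side reflects the intention. They show only that the two do not match.

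A third is that the illustration is generous. That also stands. Section 1.1 reports no positive effect of postoperative IS in the cited systematic review and no significant morbidity difference in the preoperative studies. Under Section 5.0 every patient receives a spirometer after surgery, so the contrast is preoperative IS only. Halving is a device to show direction and not a forecast.

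Two stronger readings are tempting and are not supported. A reader might infer that Section 9.6 prescribes any MAGS-graded complication against none in all three analyses. It does not name MAGS, sets no cut-point, and leaves the stepwise outcome unidentified; any against none is the natural reading but not a stated one. A reader might also infer that the pulmonary rate cannot be recovered from the data. The divisional protocol and the forms are not in the documents, so whether complication type is already recorded is unknown.

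**Conclusion.** The point holds as a mismatch of wording with a real consequence: the plan states a pulmonary objective and names no analysis that estimates a pulmonary rate. The direction of any distortion is clear if IS acts only on pulmonary events, since the broader odds ratio then lies nearer 1. Its size cannot be taken from the documents, and the figures above rest wholly on assumed rates and an assumed halving.

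It would be wrong to infer that the trial stands to lose a significant finding. Every interval calculated above includes 1, for either outcome. What is at stake is whether the reported estimate answers the stated question. This is a minor point about an exploratory item. The number of groups compared (three in the Synopsis and Section 9.1, six in Sections 2.0 and 9.6), the choice between chi-square and exact tests, and the stepwise model are separate matters that this mismatch does not decide.

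**What to change.** In Sections 9.4 and 9.6, define the outcome for this objective as at least one pulmonary complication. Fix three things before analysis: the list of qualifying events, the minimum MAGS grade, and the time window. Report the rate in each randomised preoperative group, and the odds ratio for each IS arm against control, with confidence intervals. Keep any MAGS-graded postoperative complication as a supporting analysis.

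The cost is a few lines of text and a short event list. Complication assessment is already in the Schedule of Activities, outcome collection is in Section 5.0, and a one-month follow-up form is in Section 7.0. A field for complication type is needed only if the forms lack one. The adverse-event form should not be relied on as the source, because Section 6.0 exempts events related to surgery from it.

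The downside is few events and wide intervals, and a benefit on non-pulmonary complications would appear only in the supporting analysis. If the investigators do want complications of every kind, the alternative is to reword the objective in the Synopsis and Sections 2.0 and 9.1, which gives up the pulmonary question.

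### The only adjusted complication model uses stepwise selection without naming its candidates or keeping the randomised arms in, so its arm odds ratios may be missing or exaggerated

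*Combined protocol and SAP*

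**What the plan says.** Section 9.6 (Data Analysis) plans three analyses of postoperative complications.

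- A test across the six combinations of preoperative and postoperative arm: "Chi-square test will be used to test the differences between six groups".
- An unadjusted odds ratio: "The univariate logistic regression model will estimate the odds ratio of postoperative complication". The predictor is not named.
- An optional multivariable model: "Multivariate analysis through stepwise selection will be considered to examine the relationship between binary outcome and independent predictors". The entry rule is "where a significance level of 0.3 is required to allow a predictor into the model"; the threshold for retention is looser, at 0.35.

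No candidate list is given for the third analysis, and nothing says whether the arms are candidates or must stay in. Earlier in the same section, the linear model for the lung-function changes does have a named list; it is to "adjust for the other interested variables including age, sex, smoking status, BMI, ASA, and malignancy".

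Section 9.4 sets the status of the endpoint: "Exploratory Endpoints are daily frequency of IS use and postoperative complications". On allocation, section 9.1 says: "The enrolled patients will be randomized 1:1:1 to one of three groups: control, standard IS, and digital IS + text message", followed by a second randomisation to two arms after surgery. The complication objective compares randomised groups: three in the synopsis and section 9.1, six in section 2.0.

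**The concern.** In a randomised trial, the effect of the assigned arm should be estimated whatever its p-value. A rule that admits and removes terms by p-value does not do this for any term it is free to drop.

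- **Arms are candidates.** Some trials end with no adjusted estimate for an arm. In the rest, the estimate is reported because it happened to be large enough, and its odds ratio and interval take no account of that.
- **Arms are not candidates.** The only adjusted complication model says nothing about the interventions.

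The text fits either reading. At stake is the adjusted odds ratio for complications by arm, which readers may well take as the trial's answer on clinical benefit.

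**Working it through.** **Sample size.** The plan gives no power for complications; section 9.5 sizes the trial on FEV1 alone. That figure reproduces. With 49 per group, a difference of 0.4 L, SD 0.6 and two-sided alpha 0.017, the noncentrality is 0.4 / (0.6 × √(2/49)) = 3.30, and the noncentral t gives 80.62% (stated: 80.6%). Then 49 / 0.95 = 51.6, so 52 per group and 3 × 52 = 156.

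**Inputs that must be assumed.** The background (section 1.1) gives only a complication rate of up to 50% after operations such as pancreatic and liver resection, and no pulmonary rate. Risks of 15% to 50% are therefore used. The true odds ratios, 1:1 postoperative allocation (78 per arm) and the candidate list (both arms plus the six covariates named for the linear model) are also assumptions.

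**Hand check, postoperative arm.** To enter at p = 0.30, a one-parameter term needs |z| > 1.036.

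- *No effect.* The term enters about 30% of the time, so it is absent in about 70% of trials.
- *Risk 50%, true odds ratio 0.6.* The risk in the other arm is 0.375. SE = √[1/(78 × 0.5 × 0.5) + 1/(78 × 0.375 × 0.625)] = 0.326, so the expected |z| is 0.511 / 0.326 = 1.57. P(kept) = Φ(1.57 − 1.036) + Φ(−1.57 − 1.036) ≈ 0.71, so the arm is dropped in about 29% of trials. Given that it is kept, the mean z is 1.57 + [φ(0.533) − φ(2.605)] / 0.707 = 1.57 + (0.346 − 0.013) / 0.707 = 2.04. The mean odds ratio is then exp(−2.04 × 0.326) ≈ 0.51, not 0.60.
- *Risk 15%, true odds ratio 0.7.* The other risk is 0.110, SE = 0.481 and expected |z| = 0.357 / 0.481 = 0.74. P(kept) = Φ(−0.295) + Φ(−1.777) = 0.384 + 0.038 = 0.42, so the arm is dropped in about 58%.

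**Simulation of the stepwise rule** (156 patients, arms as candidates, risks 15-50%, true odds ratios 0.6-0.7). The postoperative arm is dropped in about 31-63% of trials and the preoperative arm in about 43-59%. For the postoperative arm at a true 0.6 and 50% risk, the surviving odds ratio averages about 0.48, against 0.56 when forced in. That ratio, 0.48 / 0.56 = 0.86, agrees with the hand check (0.515 / 0.60 = 0.86).

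**Second simulation** (600-800 runs per scenario, risks 15%, 30% and 50%). The arm is coded as a three-level preoperative factor or a six-level group; the true odds ratio applies to either preoperative spirometry arm versus control.

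| True OR | Arm absent | Mean OR if kept | Mean OR if forced in | 95% CI coverage if kept |
|---|---|---|---|---|
| 1.0 | 66-73% | typically a factor 1.8-2.7 from 1, either way | 1.00-1.05 | 80-88% |
| 0.7 | 50-75% | 0.47-0.59 | 0.64-0.73 | 89-94% |
| 0.5 | 25-72% | 0.31-0.43 | 0.44-0.53 | 94-98% |

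With all terms forced in, coverage is 0.94-0.98.

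**The case against.** The strongest reply is that the plan never gives the stepwise model the job of estimating the intervention effect. The sentence speaks of predictors in general and reads naturally as a search for prognostic factors. The model is optional and the endpoint exploratory. The same section plans two analyses without selection, and under randomisation an unadjusted comparison is valid.

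Most of this stands, and it rules out three stronger readings.

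- *That the plan leaves the trial with no usable estimate of the effect on complications.* The documents do not support this. The chi-square test uses no selection, and neither does the univariate odds ratio. The reply is incomplete only because the chi-square gives no effect size and the univariate predictor is not named, so an odds ratio by arm is likely but not guaranteed.
- *That the arms do compete with age, sex and smoking for a place.* The plan does not say so. The covariate list belongs to the linear model, and the stepwise candidates are unstated.
- *That the lenient thresholds inflate false positives.* With no true effects, at least one term reaches p < 0.05 in 36.3% of stepwise trials, but also in 35.5% of trials with every term forced in. Eight independent tests would give 1 − 0.95^8 = 34%. This is multiplicity, and forcing the terms in leaves it nearly unchanged.

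Two limits on size also stand. Part of the gap between 0.48 and 0.60 is not selection, since the forced model itself averages 0.56. And interval undercoverage is clear at no effect, smaller at 0.7 and absent at 0.5.

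**Conclusion.** The concern holds in a limited form. Section 9.6 makes p-value selection the only multivariable analysis of complications, names no candidates and does not protect the randomised arms. An adjusted odds ratio by arm from this model is therefore absent by design, absent by chance (roughly a third to three-fifths of trials at true odds ratios of 0.6-0.7), or exaggerated when present (about 0.48 against 0.56 in the example).

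These sizes rest on assumed complication risks of 15-50%, assumed effects and assumed candidates, none of which the documents supply. The direction does not depend on the exact values. The primary FEV1 analysis, the sample size and the unselected complication analyses are untouched. The point is worth correcting because it is cheap, not because it threatens the trial's main conclusion.

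**What to change.** Replace the stepwise sentence in section 9.6 with a prespecified model, for example:

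*Complications will be analysed by logistic regression with preoperative arm (three levels) and postoperative arm (two levels) forced into the model, adjusted for age, sex, smoking status, BMI, ASA and malignancy, using Firth penalisation. Odds ratios for both randomised factors will be reported with 95% confidence intervals, whatever their p-values.*

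Firth penalisation should apply throughout; using it only if events turn out to be few would be another data-dependent choice. If a stepwise model is kept, label it prognostic only and do not use it for intervention effects. State also that the predictor in the univariate model is the randomised arm, if that is intended.

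The cost is SAP wording plus some precision. The model has at least 10 parameters: intercept 1, preoperative arm 2, postoperative arm 1 and covariates 6, with more if smoking status or ASA has several levels. At 15% risk there would be 0.15 × 156 ≈ 23 events, about 2.3 per parameter; at 50%, 78 events, about 7.8 per parameter. Intervals will be wide if pulmonary complications are few, and the report should say so.
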